5.3. Screening/Baseline/Run-in Failures

Screen failures are defined as subjects who consent to participate in the clinical trial but are never subsequently randomized. In order to ensure transparent reporting of screen failure subjects, meet the Consolidated Standards of Reporting Trials (CONSORT) publishing requirements, and respond to queries from Regulatory authorities, a minimal set of screen failure information is required including Demography, Screen Failure details, Eligibility Criteria, and Serious Adverse Events. Subjects can be rescreened once if agreed after discussion with the Medical Monitor.

5.4. Withdrawal/Stopping Criteria

A subject may withdraw from the study at any time at his or her own request, or may be withdrawn at any time at the discretion of the Investigator or the Sponsor for safety, behavioral, or administrative reasons. Safety data will be reviewed by the Sponsor in-stream by single case and collectively. If a safety concern arises, a decision about continuation of the study will be made.

Any subject presenting with nausea symptoms on the day of the off-therapy MRI or who had vomited within 12 hours prior to the scheduled off-therapy MRI session visit can be rescheduled for the visit or withdrawn at the Investigator's discretion.

Subjects who cannot complete any of the study procedures may be replaced at the discretion of the Investigator after consultation with the Sponsor.

A subject **MUST** be withdrawn from the study for the reasons including, but not limited to:

- Any AE, which, in the opinion of the Investigator precludes effective participation of the subject or poses a safety concern

The following AEs **will** require withdrawal:

- Confirmed pancreatitis
 - Pancreatic cancer.
 - Confirmed MTC or other thyroid C-cell neoplasia.
 - Liver chemistry abnormalities exceeding the threshold criteria outlined in [Appendix 2](#)
 - Severe allergic/hypersensitivity reactions that are considered by the Investigator to be attributable to investigational product or without a likely alternative aetiology.
 - QTc stopping criteria (see Section [5.4.2](#))
 - AE, which, in the opinion of the Investigator, requires withdrawal
 - Severe hypoglycemia, which, in the opinion of the Investigator or medical monitor, requires withdrawal
- Consent withdrawn
 - Lost to follow-up
 - Termination of study by sponsor
 - Pregnancy
 - Any untoward findings during the MRI scan that may jeopardize the imaging analysis or subject safety.

A subject **MAY** be withdrawn from the study for the reasons including, but not limited to:

- Nausea or vomiting requiring the use of anti-emetics or other interventions
- Protocol deviation (the Investigator should discuss the protocol deviation with the medical monitor before withdrawing a subject)
- Noncompliance with study visit schedule, as determined by the Investigator in consultation with the sponsor
- Other: the reason must be documented on the electronic Case Report Form (eCRF)

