4.3. Type and Number of Subjects

This study will enrol both male and female healthy volunteers 18-50 years old who are right handed and sensitive to motion sickness. Approximately 60 healthy adults will be screened to achieve a total (from Parts A and B) of 24 or 28 randomized subjects.

In Part A, approximately 10 healthy adults will be screened to achieve 4 randomized. An additional 4 subjects (Cohort 2) may be randomized if changes to the acquisition parameters and scanning paradigm require confirmation before progressing to Part B.

If subjects prematurely discontinue the study or individual subject technical issues arise, subjects may be replaced at the discretion of the Investigator or imaging evaluators in consultation with the Sponsor. Subjects will be assigned to the same treatment sequence in order to meet the target number of subjects.

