6.2. Treatment Assignment

Randomized treatment assignment will be done via web-based interactive response (IRT) system (RAMOS NG).

Subjects will be randomized to one of the 4 crossover dosing/imaging sequences in either Part A or Part B. Once the required number of subjects have been randomized e.g. Cohort 1 in Part A, randomization of additional subjects will be put on hold. Randomization will resume after decision to either enroll a second Cohort in Part A or progress to Part B has been made.

Site personnel will receive a randomization notification indicating the unique subject identifier, the treatment sequence, and the date and time of randomization. Each subject number will be a unique identifier. Once a subject number has been assigned, the number will not be reused even if the subject withdraws before receiving any randomized study medication.

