6.4. Blinding

This will be a single blind (GSK and site staff are unblinded but subjects and imaging evaluators of MRI are blinded) study and the following will apply. Evaluators in this study are staff who analyze neuroimaging data. Every attempt will be made to maintain the single-blind. Exenatide placebo is not available for this study. An injection of saline using the same needle size will be given to the subjects who will be blind-folded at the time they receive the injection.

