9.2.2. Sample Size Re-estimation or Adjustment

If subjects prematurely discontinue the study or individual subject technical issues arise, subjects will be replaced at the discretion of the imaging evaluators' judgment in consultation with the Investigator and Sponsor. Subjects will be assigned to the same treatment sequence in order to meet the target number of subjects. Within each phase or part, the randomization of subjects should first be completed before subjects are replaced. Data from subjects who are replaced will be used only for safety analysis.

Issues that may lead to exclusion of data from analysis could include excessive head-motion by the subject during a scan, identifiable artifacts on the brain images arising from problems with the scanner, and issues with the simultaneous physiological recordings (poor signals due to interference, or sensors moving out of position during a scan). Data quality will be iteratively assessed by technical imaging site staff throughout the study in a blinded manner. If some subjects' data is sub-standard and therefore needs to be excluded, additional recruiting and testing may be conducted. Data quality findings will be documented.

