4. ANALYSIS POPULATIONS

Population	Definition / Criteria	Analyses Evaluated
All Screened	
 • All participants who were screened will be considered for this population. This population will be used for summarizing screening status 	
 • Screen failure
Enrolled	
 • All participants who were successfully screened and enrolled for the trial and for whom a record exists on the study database. 	
 • Study population
Safety	
 • Comprise of all subjects who receive at least one dose of study treatment. • This population will be based on the treatment the subject actually received. • This population will include subjects who were replaced due to imaging data being invalid or not evaluable but received study drug. 	
 • Safety
Analysis Set (Randomised)	
 • Comprise of all randomized subjects who receive treatment and with valid imaging data, that will be determined by Martinos. • Subjects who are replaced are excluded from this population. 	
 • Imaging (Mechanism of Action)

NOTES :

- Please refer to Appendix 7: List of Data Displays which details the population to be used for each display being generated.

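### Protocol Sections 4.3, 5.4 and 9.2.2 give inconsistent replacement rules, and under 5.4 and one branch of 4.3 unblinded persons can decide whether a subject with usable scans stays in the imaging analysis

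*Protocol*

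**What the plan says.** Three sections of the protocol state who may replace a subject.

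- **Section 5.4:** "Subjects who cannot complete any of the study procedures may be replaced at the discretion of the Investigator after consultation with the Sponsor". The imaging evaluators have no part in this rule.
- **Section 4.3**, for early discontinuation or individual technical problems: "subjects may be replaced at the discretion of the Investigator or imaging evaluators in consultation with the Sponsor".
- **Section 9.2.2**, for the same two triggers as 4.3: "subjects will be replaced at the discretion of the imaging evaluators' judgment in consultation with the Investigator and Sponsor".

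On who knows the treatment, Section 6.4 says that "GSK and site staff are unblinded but subjects and imaging evaluators of MRI are blinded". Section 6.2 adds: "Site personnel will receive a randomization notification indicating the unique subject identifier, the treatment sequence, and the date and time of randomization".

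On the consequence of replacement, protocol Section 9.2.2 says: "Data from subjects who are replaced will be used only for safety analysis". SAP Section 4 says of the imaging Analysis Set: "Subjects who are replaced are excluded from this population". Protocol Section 9.3, by contrast, allows subjects with incomplete data to enter those analyses for which their data suffice.

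**The concern.** Replacement here is more than a recruitment matter, because it also removes the replaced subject from the imaging analysis. Whoever decides on replacement therefore helps to decide who is analysed. The protocol blinds the people who analyse the images and presents this as a main design feature, yet two of its three replacement rules let the decision be taken by people who know the treatment.

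The grounds may also be related to the outcome. Nausea is the effect under study, and Section 5.4 lists nausea or vomiting that needs intervention among the optional reasons for withdrawal. Withdrawal is an early discontinuation, which opens the way to replacement under 4.3 and 9.2.2. If replacement decisions depend on how a subject tolerated a drug that the decider can identify, the analysed group may differ systematically from the randomized group.

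**Working it through.** The documents give no replacement rate, no effect size and no standard deviation for the imaging endpoints, so no bias can be calculated. The check is a comparison of the texts.

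**Step 1. The three rules side by side.**

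| | 4.3 | 5.4 | 9.2.2 |
|---|---|---|---|
| Trigger | Early discontinuation or technical problem | Inability to complete study procedures | Early discontinuation or technical problem |
| Decider | Investigator or imaging evaluators | Investigator | Imaging evaluators |
| Consulted | Sponsor | Sponsor | Investigator and Sponsor |
| Force | *may* | *may* | *will* |
| Blinded decider? | Only if the evaluators decide | No | Yes, but unblinded parties are consulted |

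No section says which rule prevails.

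**Step 2. Is the Investigator unblinded?** No sentence says so by name. It follows from Section 6.4, which leaves site staff unblinded, and from Section 6.2, which sends the sequence to site personnel. Under 5.4, then, both the decider and the party consulted know the treatment.

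**Step 3. Does replacement change who is analysed?** Yes, for some subjects. Take sequence 3, in which Session 1 contains the off-therapy scan and the post-exenatide scan. A subject who leaves before Session 2 has both scans for the exenatide versus off-therapy contrast named in Section 9.3. If not replaced, the subject may contribute to that contrast. If replaced, the subject is lost to it under 9.2.2 and SAP Section 4, however good the scans are. The same holds in sequence 1 for albiglutide versus off-therapy. A subject with all scans who failed some other procedure could lose every contrast under the wider reading of 5.4 (Step 4).

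**Step 4. How wide is the 5.4 trigger?** The phrase about subjects who cannot complete any of the procedures can mean that they complete none, or that they fail at least one. On the first reading 5.4 is narrow, and such a subject has no imaging data to lose. On the second, a missed questionnaire or a failed electrogastrogram (EGG) would suffice, although Section 7.3.5 calls EGG collection during the MRI experimental. The text does not settle which is meant.

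**Step 5. Do other provisions close the gap?**

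- Blinded quality assessment in 9.2.2 covers the quality of images and recordings. It does not govern the Investigator's discretion in 5.4 or 4.3.
- SAP Section 4 lets the imaging laboratory judge whether imaging data are valid, but separately excludes every replaced subject, valid data or not.
- The SAP's Safety population describes replaced subjects as those whose imaging data were invalid or could not be evaluated. That presumes an imaging reason, which the protocol does not require.

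**Step 6. What analysis is exposed?** Part B was cancelled and four subjects completed Part A. SAP Section 2.1 records a decision not to complete the group analysis. SAP Attachment 11 nevertheless still specifies a group paired t-test of off-therapy against exenatide for resting-state data. In a set of four, one subject is 1/4 = 25% of the set. That describes the composition of the set and is not an estimate of bias. The documents do not say whether anyone was replaced.

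**The case against.** The strongest reply is that this is a wording inconsistency in a terminated exploratory study without a pre-specified hypothesis. Section 4.3 already names the evaluators as a possible decider. Discretion arises only for subjects with some failure or discontinuation. A subject without scans on both drugs has no albiglutide–exenatide difference to lose. Attachment 11 specifies no albiglutide–exenatide imaging test. The SAP already plans listings of randomized and actual treatments, withdrawal reasons and subjects excluded from populations (Listings 1, 2 and 4). Most of this stands, and it keeps the point small. It does not remove it: the rules conflict, and contrasts of drug against off-therapy can lose usable scans (Step 3).

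A reader might also infer more than the documents support:

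- **That the evaluators' blinding is broken.** A replacement decision by the Investigator does not give the evaluators a treatment code, and blinded quality assessment continues.
- **That 9.2.2 is a fully insulated rule.** It requires consultation with two unblinded parties.
- **That missing one minor procedure is certainly enough under 5.4.** This is one of two possible readings.
- **That the bias has a known size or direction.** Any figure would need an assumed replacement rate and an assumed correlation between nausea and the imaging contrast, and the documents supply neither. A calculation that replaces the most nauseated subjects would show the effect of outcome-related replacement, and would give the same answer whether the decider is blinded or not.

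**Conclusion.** The inconsistency is real. Decider, trigger and force differ across the three sections, and the 5.4 trigger is ambiguous. Under 5.4, and where the Investigator decides under 4.3, persons who know the treatment can determine whether a subject with usable scans is in the imaging analysis, possibly for reasons linked to drug-induced nausea. This rests on the inference that the Investigator is among the unblinded site staff.

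The size and direction of any bias cannot be derived. Practical impact is limited, because Part B was cancelled and SAP Section 2.1 drops the group analysis. The paired test left in Attachment 11 is the one specified group imaging comparison that replacement could still affect.

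**What to change.** Put one rule in Sections 4.3, 5.4 and 9.2.2:

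1. The blinded imaging evaluators decide on replacement, before any treatment code is used.
2. The only ground is that a required MRI acquisition is missing or unusable.
3. The Investigator and Sponsor report discontinuations but do not choose whom to replace.
4. Missing EGG, questionnaire or other non-imaging data is not a ground for replacement.

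Delete the separate replacement sentence in 5.4 and leave the withdrawal criteria as they are. In the SAP, add the reason for replacement and the sequence to the existing listing of subjects excluded from populations (Listing 4).

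The cost is protocol wording and two items in a planned listing. The downside is that the Investigator loses some discretion over replacements. The rule does not make missing scans independent of nausea, since a subject too nauseated to be scanned would still qualify, and discretionary withdrawal remains. It does take the choice of whom to replace away from those who know the treatment. As Part A is complete, the listing is the part that can still inform a reader of this study's results.

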5.4.1. Liver Chemistry Stopping Criteria

Liver chemistry stopping and increased monitoring criteria have been designed to assure subject safety and evaluate liver event etiology (in alignment with the FDA premarketing clinical liver safety guidance).

<http://www.fda.gov/downloads/Drugs/GuidanceComplianceRegulatoryInformation/Guidances/UCM174090.pdf>

Liver Safety Required Actions and Follow up Assessments Section can be found in [Appendix 2](#).

5.4.2. QTc Stopping Criteria

A subject that meets either bulleted criterion below will be withdrawn from the study.

- QTcF >500 msec,
- Change from baseline: QTcF >60 msec

5.4.3. Withdrawal Procedures

Subjects who withdraw from the study before completion of all procedures and assessments must complete all assessments for the follow-up visit (see Time and Events Table, Section 7.1).

The following actions must be taken in relation to a subject who fails to attend the clinic for a required study visit:

- The site must attempt to contact the subject and re-schedule the missed visit as soon as possible.
- The site must counsel the subject on the importance of maintaining the assigned visit schedule and ascertain whether or not the subject wishes to and/or should continue in the study.
- In cases where the subject is deemed 'lost to follow up', the Investigator or designee must make every effort to regain contact with the subject (where possible, 3 telephone calls and if necessary a certified letter to the subject's last known mailing address or local equivalent methods). These contact attempts should be documented in the subject's medical record.

- Should the subject continue to be unreachable, only then will he/she be considered to have withdrawn from the study with a primary reason of “Lost to Follow-up”.

5.5. Subject and Study Completion

A completed subject is one who has completed all scheduled visits including follow-up.

Study Completion is defined as the last subject’s last visit.

6. STUDY TREATMENT

6.1. Investigational Product and Other Study Treatment

The term ‘study treatment’ is used throughout the protocol to describe any combination of products received by the subject as per the protocol design. Study treatment may therefore refer to the individual study treatments or the combination of those study treatments.

	Study Treatment			
Product name:	Albiglutide (GSK716155)	Matching albiglutide placebo	Exenatide (Byetta)	Exenatide placebo (saline)
Formulation description:	Single-use fixed dose, fully disposable pen injector system for SC delivery	Single-use fixed dose, fully disposable pen injector system for SC delivery	A sterile solution containing 250 µg /mL exenatide	Sterile saline
Dosage form:	50 mg pen: Contains 67 mg lyophilised albiglutide and 0.65 mL diluent designed to deliver a dose of 50 mg in a volume of 0.5 mL after reconstitution.	NA	10 µg per dose in 2.4 mL prefilled pen. One dose will be used.	NA
Unit dose strength(s)/Dosage level(s):	50 mg in 0.5 mL injector volume	0.5 mL injector volume	10 µg per dose in 2.4 mL prefilled pen	0.04 mL
Route of Administration	SC	SC	SC	SC

	Study Treatment			
Dosing instructions:	To be reconstituted as directed in the SRM. Inject SC in the upper arm.	To be reconstituted as directed in the SRM. Inject SC in the upper arm.	Follow new pen set-up in prescribing information. Inject SC in the upper arm.	Inject SC in the upper arm.

6.2. Treatment Assignment

Randomized treatment assignment will be done via web-based interactive response (IRT) system (RAMOS NG).

Subjects will be randomized to one of the 4 crossover dosing/imaging sequences in either Part A or Part B. Once the required number of subjects have been randomized e.g. Cohort 1 in Part A, randomization of additional subjects will be put on hold. Randomization will resume after decision to either enroll a second Cohort in Part A or progress to Part B has been made.

Site personnel will receive a randomization notification indicating the unique subject identifier, the treatment sequence, and the date and time of randomization. Each subject number will be a unique identifier. Once a subject number has been assigned, the number will not be reused even if the subject withdraws before receiving any randomized study medication.

6.3. Planned Dose Adjustments

There are no planned dose adjustments in this study.

6.4. Blinding

This will be a single blind (GSK and site staff are unblinded but subjects and imaging evaluators of MRI are blinded) study and the following will apply. Evaluators in this study are staff who analyze neuroimaging data. Every attempt will be made to maintain the single-blind. Exenatide placebo is not available for this study. An injection of saline using the same needle size will be given to the subjects who will be blind-folded at the time they receive the injection.

6.5. Packaging and Labeling

The contents of the label will be in accordance with all applicable regulatory requirements.

6.6. Preparation/Handling/Storage/Accountability

- Only subjects enrolled in the study may receive study treatment and only authorized site staff may supply or administer study treatment. All study treatments must be stored in a secure environmentally controlled and monitored

(manual or automated) area in accordance with the labelled storage conditions with access limited to the Investigator and authorized site staff.

- The Investigator, institution, or the head of the medical institution (where applicable) is responsible for study treatment accountability, reconciliation, and record maintenance (i.e. receipt, reconciliation and final disposition records).
- Further guidance and information for final disposition of unused study treatment are provided in the Study Reference Manual (SRM).
- Under normal conditions of handling and administration, study treatment is not expected to pose significant safety risks to site staff. Take adequate precautions to avoid direct eye or skin contact and the generation of aerosols or mists. In the case of unintentional occupational exposure notify the monitor, Medical Monitor and/or GSK study contact.
- A Material Safety Data Sheet (MSDS)/equivalent document describing occupational hazards and recommended handling precautions either will be provided to the Investigator, where this is required by local laws, or is available upon request from GSK.

Albiglutide and matching albiglutide placebo

Albiglutide will be reconstituted as directed in the SRM. Albiglutide (and matching albiglutide placebo) is provided as a fixed-dose, fully disposable pen injector system for delivery of the investigational product (albiglutide or matching albiglutide placebo) from a prefilled dual chamber glass cartridge that is an integral part of the pen. It is intended for single use. The pen is designed for manual reconstitution of the dose, priming and insertion of the pen needle. Albiglutide s.c. injection or placebo of albiglutide s.c injection will be administered by the site staff.

Exenatide and placebo (saline)

A description of the methods and materials required for dosing of exenatide is provided in the SRM.

Sterile saline s.c. as the exenatide placebo will be administered and will be detailed in the SRM.

Exenatide s.c. injection or placebo of exenatide s.c injection will be administered by the site staff.

